2 INTRODUCTION

2.1 Study Rationale

At-home intracervical insemination (ICI), folklorickly known as the "turkey-baster" method, has been used for decades to increase likelihood of pregnancy. This method works by depositing semen close to or at the cervix. While there are several devices such as over the counter syringes and silicone caps, the creator of the Mosie Baby syringe believes it is designed to be more ergonomic and compatible with a woman's body, easy and safe to use, and results in depositing the semen at or near the cervix opening. The Mosie Kit provides people with an at-home intracervical insemination option which could be used before resorting to more invasive and expensive options such as Intrauterine Insemination (IUI) or in vitro fertilization. There is vast evidence of Mosie's success in the form of happy users who have conceived. There is a desire to learn more about the safety, useability and experience of using the Mosie kit.

This retrospective study will examine the experience of people who have voluntarily chosen to purchase and use the Mosie Kit. The Mosie Kit consists of 2 syringes and a semen collection cup Understanding the safety, useability and experience of using the Mosie Kit will provide additional information about the nature of using intracervical insemination as a viable method for getting pregnant. The information gained will increase understanding of how viable the Mosie Kit is as a first step in trying to conceive and how it is perceived by the people who have chosen to use it.

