Since [name] sperm freezing success in 1953 with a subsequent live birth, collecting and using sperm for insemination in humans was made possible. However, it would be more than a decade before it became legally possible as it was initially ruled as contrary to public policy and good morals. In the 1960s and 70s, sperm selection and washing techniques led to Intrauterine insemination (IUI) which placed the sperm even further into the woman's body by putting it directly into the uterus. By the 1970s sperm banks in the US became popular. Also in the 1970s, Steptoe and Edwards introduced the world to In-Vitro Fertilization (IVF). More recently, techniques such as intratubal insemination, and intraperitoneal insemination have been added to the available conception methods. During the last decades the popularity of Intrauterine Insemination (IUI) increased because it was safer, painless, and more cost-effective. Additionally, more information has become available about sperm selection techniques and now there is a greater understanding of many of the causes of infertility.

The most popular method of insemination is to use the husband's sperm (Artificial Insemination by Homologous or Husband (AIH)). In some cases anonymous donor sperm is used. Intracervical (ICI) or intravaginal insemination (IVI) are terms used interchangeably to describe the insemination technique colloquially known as the "turkey baster method". This method consists of placing the semen into the vagina at or near the cervix. In the United States, IUI is the most frequently doctor assisted technique. Some researchers have examined the success rates of each technique. ICI/IVI has been found to have a per cycle pregnancy rate of 10-15% while IUI has been found to be slightly higher up to 10-35%. Meanwhile techniques such as IVF can be as high as 31% in people under 35 years of age and as low as 3% for those above 43 according to the CDC.

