2.3.2 Known Potential Benefits

The potential benefit of this study is mostly for people seeking to perform at-home intracervical insemination in the future using the Mosie Kit. Each Mosie Kit provides syringes for two inseminations to occur within a cycle at the cost of about \$89. This is less than 20% of the cost of IUI which can range between \$500-1500/ procedure before labs, ultrasounds, and additional expenses, and around 5% once all costs are added up. The study will provide valuable information to people trying to conceive about the efficiency of using the Mosie Kit for ICI, how that efficiency might compare to the effectiveness of IUI, and how the cost of each compares. This will help the user decide whether the Mosie Kit is the right conception tool for them. The study will also provide valuable information about the safety and usability of the kit. The research will let Mosie know if they have successfully communicated how to use the kit, if the instructions are clear or if any changes are needed, and whether anything else should be considered in future design changes. The study might also provide information on the timing of the insemination that might lead to a positive pregnancy outcome. Additionally, this knowledge might provide Mosie Baby with information to help it position itself better in the market..

The participant themselves will only benefit by having been able to share their experience about the Mosie Kit. While they might receive a discount code towards the purchase of a future Mosie Kit, this is not considered a benefit but a thank you for participation. Note the discount code will be a standard code used for other marketing purposes in order to ensure there is no way for Mosie staff to know if the participant obtained it for completing the survey or obtained it via other marketing avenues. The participant may feel good because they shared their experience and provided input into the Mosie Kit which will in turn help others.

The information obtained through this study will allow Mosie Baby to enhance or clarify the instructions provided with the Mosie Kit and will be considered in future production of the Mosie Kit.

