Analysis: Descriptive statistics will be used to analyze perceived safety. Qualitative analysis will be used on any comments made related to safety. Rates of vaginal infections will be analyzed using descriptive statistics.

Secondary Hypothesis 5: The majority of participants indicate they have little to no safety concerns related to using the Mosie Kit. Alternative hypothesis is the majority of participants will be very concerned or extremely concerned about the safety of using the Mosie Kit.

Analysis: Descriptive statistics of self-reported level of concern. Additionally, safety measures such as hand washing, disposing of the syringe after use, and reading the instructions will be examined using descriptive statistics.

Tertiary Hypothesis 1: There will be higher pregnancy rates when using the Mosie Kit when the source of infertility is male-based than when it is female-based. The alternative hypothesis is there will be lower pregnancy rates when using the Mosie Kit when the source of infertility is male-based than when it is female-based.

Analysis: In addition to the descriptive statistics a t-test will be run to examine this hypothesis.

Tertiary Hypothesis 2: There is a difference in pregnancy rates of people with known fertility issues depending on the source of their infertility. Specifically, the following sources of infertility will be examined if sufficient data is available.

- o PCOS
- Endometriosis
- Low AMH or low ovarian reserve
- Low sperm count
- Sperm motility issues
- Unexplained infertility
- Erectile dysfunction
- Performance issues or sexual anxiety, or inability to orgasm with partner.

Page 27

- Vaginismus or vulvodynia
- Tilted uterus
- Multiple uterus/cervix
- Loss of a fallopian tube

The alternative hypothesis is that there will be no difference in the fertility rates associated with different sources of infertility.

Analysis: Descriptive statistics, t-test, correlations and multiple ANOVAs will be used to examine this hypothesis.

Tertiary Hypothesis 3: There will be a difference between individuals who perform 2 insemination instances as described in the instructions and those that follow a different schedule or dosage number. The alternate hypothesis is that there will be no difference between the individuals that perform the minimum 2 insemination instances and those that follow difference dosage schedule.

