Analysis: Descriptive statistics of pregnancy rates for groups with 1, 2, 3 and 4 or more inseminations per cycle will be used. These rates will then be compared to determine if there is a difference.

Tertiary Hypothesis 4: COVID-19 has affected people's family expansion plans. The alternate hypothesis is that COVID-19 has had no effect on people's family expansion plans.

Analysis: Descriptive analysis and a t-test will be conducted to examine this hypothesis.

Tertiary Hypothesis 5: There will be a decrease in pregnancy rates in those using the Mosie Kit during the Months of March - June.

Analysis: Descriptive statistics, graphing, ANOVA and multiple regression analysis will be used to examine this hypothesis.

Additional Analysis will also be conducted to explore why people might choose to use the Mosie Kit, how they actually use it, additional things they do when using the Mosie Kit to complement the experience, and whether they think their health care provider should recommend Mose as an conception option. Most of this analysis will be achieved using descriptive statistics, correlations, and t-tests.

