[figure not shown]
How did you or your partner time your ovulation? (Select all that apply.) *
Count days in cycle
Track vaginal or cervical fluids
Tracking changes in the cervix
Use ovulation predictor kit
Use an app to estimate ovulation
Basal Body Temperature
Wearable device
Did not time ovulation
Did using Mosie result in a pregnancy? *
O Yes
O No
Back Next Page 10 of 20

[figure not shown]
Never submit passwords through Google Forms.

 $This \ content \ is \ neither \ created \ nor \ endorsed \ by \ Google. \ \underline{Report \ Abuse} - \underline{Terms \ of \ Service} - \underline{Privacy \ Policy}$

Google Forms

Page 56

[figure not shown]

Safe process

Enjoyable

	Very Easy	Easy	Neutral	Difficult	Very Difficult
To collect the semen/sperm sample in the cup?	0	0	0	0	0
To draw up the semen/sperm in the syringe?	0	0	0	0	0
Insert the Mosie syringe into the vagina up to the handles?	0	0	0	0	0
To deposit the semen/sperm at or near the cervix using the syringe?	0	0	0	0	0
My overall impression on the ease of use	0	0	0	0	0
					Page 12 of 20
submit passwords to	through Google Fo				

MOSIE-001 © 2020 Mosie Baby Page 59

MOSIE-001 © 2020 Mosie Baby

Page 60

Pulled the syringe plunger back and forth to confirm it was functioning.

My partner washed their hands

Use a sperm friendly-lubricant.

Thawed out donor sperm from sperm bank

Prepared all items and have them handy ready to use.

Washed the penis

that	apply)?*
	Lie down in a comfortable position.
	Relax
	Receive oral sex
	Stimulate clitoris
	Use any vibratory or non-vibratory stimulation device intravaginally
	Have an orgasm
	Other:
	erall, how well were you able to use the Mosie syringe to inseminate yourself our partner? * Very Able
	our partner? *
or y O O O	our partner? * Very Able Able Not Very Able
or y 0 0 0 0	Very Able Able Not Very Able Not Able at All Volume at All Volume at All Volume at All Volume at All Able at All Volume at All Able at All Able at All
or y O O O	Very Able Able Not Very Able Not Able at All Volong did you remain laying down after using the Mosie syringe? * Less than 15 minutes

Willelf best descri	ibes your lying position? *	
On my stomach	n	
On my side		
On my back		
On my back wit	th my hips elevated by a pillow	
Other:		
O No		
O		
What type of sam	ple did you use? *	
What type of sam	ople did you use? * rom a sperm bank (frozen)	
What type of sam	rom a sperm bank (frozen)	

0 2000	thank 50%	
O 51%-	70%	
O 71% -	80%	
O 81%-	90%	
O 90%-	95%	
O 96%-	100%	

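### Tertiary Hypothesis 3 compares people by inseminations per cycle without fixing a cycle denominator, so unequal numbers of cycles can understate or reverse a true difference

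*Combined protocol and SAP*

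**What the plan says.** Section 9.1 states the hypothesis about people: "There will be a difference between individuals who perform 2 insemination instances as described in the instructions", set against those who follow another schedule or number. The analysis is two sentences: "Descriptive statistics of pregnancy rates for groups with 1, 2, 3 and 4 or more inseminations per cycle will be used", then "These rates will then be compared to determine if there is a difference". It names no denominator, no test, no allowance for the number of cycles a person tried, and no rule for someone whose count differs between cycles.

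The legible outcome item in Appendix A is a single Yes/No: "Did using Mosie result in a pregnancy". Use is recorded cycle by cycle. The legible grid has four timing windows, each scored 0, 1, 2 or 3+, and is followed by a question on whether another cycle was tried. The skip logic refers to cycles 2 to 6. Respondents therefore contribute between one cycle (section 5.1) and six (section 3).

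On the product, section 2.1 says "The Mosie Kit consists of 2 syringes and a semen collection cup", and section 2.3.2 says "Each Mosie Kit provides syringes for two inseminations to occur within a cycle".

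**The concern.** The exposure belongs to a cycle, and the outcome, as legible, belongs to a person over all cycles. A person who tries more cycles has more chances to conceive, whatever number of inseminations is done in each. If the number of cycles differs between the groups, the comparison mixes the effect of inseminations per cycle with the effect of having tried longer.

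There is a specific reason to expect such a difference. A two-syringe kit covers one cycle at two inseminations, or two cycles at one. Cycles available per kit therefore run against the exposure, which favours the one-per-cycle group.

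The grouping is also incomplete. Someone who used one insemination in the first cycle and two in the next belongs to both groups or to neither.

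Section 4.2 says the findings on timing and dosing should lead to clearer instructions and better use of the kit by all users. A result that pointed the wrong way because of cycle counts alone would feed into that.

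**Working it through.** **The plan's own figures.** None is given for this hypothesis: no sample size, effect size or power. The only precision figure, in section 9.2, is for a proportion in the whole sample, and it reproduces: 1.96 × √(0.25/500) = 4.4%. It does not bear on this comparison.

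**Inputs.**
- Syringes per kit: 2 (sections 2.1 and 2.3.2).
- Cycles covered by the survey: at most 6 (section 3, Appendix A).
- Per-cycle pregnancy rate: section 2.2 says "ICI/IVI has been found to have a per cycle pregnancy rate of 10-15" per cent. The documents give no rate by number of inseminations. I assume 10% with one and 15% with two, the ends of that range, purely as an illustration.
- Kits per user: not given. I assume equal kits in both groups, shown for 1 to 4 and for 6.
- Also assumed: no syringe is used twice, and every syringe is used unless pregnancy comes first.

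**Formula.** The chance that a person conceives within c cycles is 1 − (1 − p)^c. With k kits, c = 2k at one insemination per cycle and c = k at two, each capped at 6.

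| Kits | One per cycle, p = 10% | Two per cycle, p = 15% | Order |
|---|---|---|---|
| 1 | 1 − 0.90² = 19.0% | 15.0% | reversed |
| 2 | 1 − 0.90⁴ = 34.4% | 1 − 0.85² = 27.8% | reversed |
| 3 | 1 − 0.90⁶ = 46.9% | 1 − 0.85³ = 38.6% | reversed |
| 4 | 46.9% (cap of 6) | 1 − 0.85⁴ = 47.8% | almost equal |
| 6 | 46.9% (cap of 6) | 1 − 0.85⁶ = 62.3% | correct |

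**Thresholds.**
- One kit, p = 10% with one insemination: break-even for two is 1 − 0.90² = 19.0%, a per-cycle ratio of 1.9. Any smaller true benefit is reversed.
- For 10% against 15%, reversal needs a ratio of cycles above ln 0.85 / ln 0.90 = 1.54.
- One kit, where only a share m of one-per-cycle users would go on to a second cycle: their rate is 0.10 + 0.09m, which exceeds 0.15 only if m is above 0.05/0.09 = 56%.
- No true effect (10% in both groups), one kit: 19.0% against 10.0%, a spurious difference.

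**The same example per cycle started.** With one kit, the one-per-cycle group expects 0.19 pregnancies over 1 + 0.90 = 1.90 cycles, which is 10%. The two-per-cycle group expects 0.15 over 1 cycle, which is 15%. With three kits the results are again 10% and 15%. The cycle denominator recovers the assumed rates.

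**The case against.** **The denominator is unstated, not stated to be persons.** The analysis sentence groups by a per-cycle count and never says that pregnancies are divided by people. The plan uses cycle denominators elsewhere: for insemination timing under Secondary Hypothesis 3 and for infections in section 8.3. This stands as far as it goes. But the hypothesis speaks of individuals, the legible outcome is per person, and where the plan wants cycles it says so. Nothing commits the analyst to cycles here.

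**A reader might infer that one-per-cycle users do have twice as many cycles.** The documents do not support that. It holds per kit, and per person only with equal kits, no reuse and both syringes used in separate cycles. The planned groups of 3 and of 4 or more imply that some users had several kits or reused syringes. Section 9.1 treats "disposing of the syringe after use" as a behaviour to be examined, not as established.

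**A reader might also infer that the pregnancy cannot be traced to a cycle.** This too is unsupported. Appendix A says pregnant respondents receive further questions, and some survey screens are not shown, so the conception cycle may be recorded.

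**Section 9.4.3 lists number of inseminations and number of cycles in an exploratory model of pregnancy.** So the data could support an adjustment. That model is not tied to this hypothesis, and its stated methods are correlations and goodness-of-fit tests. A person's total cycles is also cut short by conceiving, so entering it as a person-level covariate is not equivalent to a per-cycle analysis.

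**The hypothesis is tertiary.** True. Neither the primary endpoint nor the sample size is affected.

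**Conclusion.** The point holds as a gap in specification with a plausible direction of bias. As written, Tertiary Hypothesis 3 sets a cumulative Yes/No over one to six cycles against a per-cycle exposure, with no fixed cycle denominator and no rule for people whose count varies. This can understate or reverse a true benefit of two inseminations, or create a difference where none exists.

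In the illustration the order is reversed through three kits per person and the benefit is almost erased at four; with six kits the order is correct. That rests on assumed rates of 10% and 15%, equal kits, single-use syringes and full use of them. The documents give no kits-per-user figure, so the actual size is unknown, and a reader should not infer that the study's result will be reversed. Nor does the illustration say anything about how many inseminations are advisable.

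**What to change.** Reword Tertiary Hypothesis 3 in sections 4.1 and 9.1 from individuals to cycles, and make each reported cycle one record.

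- **Exposure:** the insemination count for that cycle, summed over the four windows of its timing grid. The top score of 3+ cannot always separate 3 from 4 or more, so state a rule for those cycles.
- **Outcome:** assign the pregnancy to the conception cycle if the survey records it. Otherwise assign it to the last recorded cycle, and state this as an assumption.
- **Analysis:** report pregnancies per cycle started for each count, and compare counts with a discrete-time logistic model containing cycle number and age. Respondent-clustered standard errors are optional, since each respondent has at most one event under this set-up.

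People whose count changes between cycles then contribute each cycle to the group where it belongs.

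The cost is the rewording and reshaping the data to one row per cycle. No new survey question is needed. The downside is possible misassignment under the last-cycle rule, for example when someone conceived, lost the pregnancy and resumed use.

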6.1.2 Administration and/or Dosing

This study retrospectively examines the administration and dosing of semen during insemination in the home environment by using the Mosie Kit. The recommended dosing of semen to produce a positive pregnancy outcome is at least 2 times in a cycle. With the first dose preferably administered within 24 hours of the first signs of ovulation and the second one between 24-48 hours post ovulation confirmation. Since this study is retrospective, it will not influence dosing, but merely will collect information on the dosing frequency and timing.

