6.4 Study Intervention/Experimental Manipulation Adherence

This study does not have an intervention. However data will be collected on the self-administered intervention that will be examined retrospectively. The data will allow determination as to whether the minimum intervention was followed, i.e. administration of two

at-home insemination instances one within 24 hours of initial signs of ovulation and one at 24-48 hours after confirmed ovulation.

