Analysis: Descriptive statistics surrounding the ease of use on a 5-point likert (very easy to very difficult) will be analyzed on five different aspects of use. Specifically, the steps of using the Mosie Kit (collecting a sperm sample, drawing up the sample in the Mosie syringe, inserting the syringe, and depositing the sperm at or near the cervix) and overall ease of use will be examined. Additionally questions related to use such as comfort, ease and safety of the process, enjoyable and intuitiveness of use (able to use it without instructions) will allow the user to rate their experience from Strongly agree to strongly disagree (5 point scale). The data will be plotted and examined as part of the analysis.

Secondary Hypothesis 2: The participants were able to use the Mosie Kit as instructed using the instructions contained in the kit. The alternative hypothesis is that the participants were not able to use the kit using the instructions contained in the kit.

Analysis: Descriptive analysis of perceived overall success rate will be analyzed. Additionally, descriptive analysis of the frequency of each expected behavior related to use of the kit will be examined.

Secondary Hypothesis 3: The participants reported they used the kit as intended, specifically, using it within 24 hours of initial signs of ovulation and again 24-48 hours after ovulation was confirmed or expected. The alternative hypothesis is that the participants report they did not use the kit as intended with respect to timing (within 24 hours of initial signs of ovulation and again 24-48 hours post ovulation).

Analysis: Frequency rates related to timing of insemination at all reported cycles will be analyzed. The data will be reported in both total number of attempts at each time point as well as percentage of attempts at each time point in comparison with total cycles where the Mosie Kit was used. T-tests will also be used in this analysis. Additionally,

amount of time lying after insemination and position of lying will be analysed using descriptive statistics and correlations with pregnancy rate.

Secondary Hypothesis 4: Participants reported they perceived the Mosie Kit to be a safe way to conceive. The alternative hypothesis is that participants did not perceive the Mosie Kit to be a safe way to conceive.

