9.4.3 Exploratory Analyses

Additional exploratory data analysis will be conducted to examine the main characteristics of the data. This analysis will be done using descriptive statistics, scatter plots, and odds ratio. If the exploratory analysis warrants the testing of new hypotheses, t-test or ANOVA may be used for further analysis.

Exploratory modeling will be conducted to examine multiple variables and their relationship to the pregnancy outcome. This will include the source of infertility, age, number of inseminations, number of cycles, lying time, and type of relationship. The model will use correlations and goodness of fit tests in its analysis.

1 0 SUPPORTING DOCUMENTATION AND OPERATIONAL CONSIDERATIONS

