10.1.8 Quality Assurance and Quality Control

This one time survey does not require clinical monitoring or an external QA process. Quality Assurance is conducted to ensure the quality of data is complete and that appropriate documentation is in place to support and conduct the study.

Quality Control (QC) Procedures will be implemented as follows:

- Informed Consent PI and Sponsor will both review the documentation of the
 consenting process. This review will be conducted in compliance with GCP, accuracy
 and completeness. Feedback will be provided to the PI and Sponsor in order to ensure
 proper consenting procedures are followed. The Institutional Review Board will also
 review and provide feedback on this process.
- Source Documents and the electronic data The electronic data capture will constitute the source documents for this study. The data will be entered by the participant directly into the final study database.
- Intervention fidelity This is a retrospective observational study of people using the
 Mosie Kit. Part of data collection will include information about the use of the kit and how
 it was used. This information will be used to determine whether the person used the kit
 as intended thus confirming the intervention fidelity occurred voluntarily prior to
 participation in the study.
- Protocol Deviations There is no directed intervention for this study. Therefore, protocol deviations with respect to an intervention are not expected. If any deviations occur with relation to how the data is collected or the participants recruited, that will be collected as part of the study documentation.

There is no expectation that independent monitoring would be necessary. However, if it is required, the necessary arrangements will be made.

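### Tertiary Hypothesis 3 is about following the instructed two-insemination schedule, but its analysis groups by count only and no named analysis relates insemination timing to pregnancy

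*Combined protocol and SAP*

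**What the plan says.** Section 9.1 sets up Tertiary Hypothesis 3 as a contrast of "individuals who perform 2 insemination instances as described in the instructions and those that follow a different schedule or dosage number". Its second sentence, which gives the alternate, is worded differently. It speaks of no difference between "the individuals that perform the minimum 2 insemination instances and those that follow difference dosage schedule".

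The analysis for this hypothesis is: "Descriptive statistics of pregnancy rates for groups with 1, 2, 3 and 4 or more inseminations per cycle will be used". The count-group rates are then to be compared, with no test named.

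The instructed schedule is described in several places. Section 6.1.2 says "The recommended dosing of semen to produce a positive pregnancy outcome is at least 2 times in a cycle", and adds a preferred window for the first insemination and a 24-to-48-hour window for the second. Section 6.4 says "The data will allow determination as to whether the minimum intervention was followed", and puts both windows into that minimum. Section 10.1.8 adds, on intervention fidelity, "This information will be used to determine whether the person used the kit" as intended.

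Timing also appears under Secondary Hypothesis 3, which reports how often inseminations fell at each time point. There the plan says "T-tests will also be used in this analysis" without naming the variables. The only link to pregnancy stated there is for lying time and lying position. For the exploratory model of pregnancy in Section 9.4.3: "This will include the source of infertility, age, number of inseminations, number of cycles, lying time, and type of relationship".

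**The concern.** The hypothesis names two ways of departing from the instructions: a different schedule or a different number. The analysis can see only the second. Someone who inseminated twice in a cycle, but outside the instructed windows, belongs with the comparator under the hypothesis. Under the analysis, that person sits in the two-per-cycle group with those who followed the instructions.

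At stake is what the tertiary result can be taken to mean. The two-per-cycle rate could be reported as the rate for users who followed the instructions, which it is not. The protocol does show an interest in timing. Section 4.2 says one of the tertiary hypotheses will collect information on both timing and dosing, Section 6.2 hopes to learn whether timing and frequency played a role in pregnancy, and Section 2.3.2 lists timing among the possible benefits.

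**Working it through.** **The plan's own figures.** None is given for Tertiary Hypothesis 3. The precision figures in Section 9.2 reproduce: 1.96 × √(0.25/500) = 4.38%, against the stated 4.4%, and 1.96 × √(0.25/384) = 5.00%, against the stated 5%. They concern a single overall proportion and do not bear on this point.

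**Step 1: does any analysis relate insemination timing to pregnancy?**

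| Place | Insemination timing used? | Set against pregnancy? |
|---|---|---|
| 9.1, Tertiary Hypothesis 3 | No, count only | Yes |
| 9.1, Secondary Hypothesis 3 | Yes, frequencies and percentages | Not for timing; lying time and position only |
| 9.1, Secondary Hypothesis 3 t-tests | Variables not stated | Not stated |
| 9.1, Tertiary Hypothesis 5 | No, calendar months | Yes |
| 9.1, additional analysis | How the kit is used, in general terms | Not named |
| 9.4.1, correlations | Variables not stated | Not stated |
| 9.4.2, subgroups | Not listed | Yes, for listed factors |
| 9.4.3, exploratory model | Not listed; number of inseminations is | Yes |
| 6.4 and 10.1.8, adherence status | Yes, in 6.4; use as intended in 10.1.8 | No analysis of that status named |

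No row names both. Section 9.4.1 says the analysis for each hypothesis has already been set out in Section 9.1, and for this hypothesis that is the count comparison.

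**Step 2: what the two-per-cycle group contains.** The timing grid visible in Appendix A has four rows: 24 to 48 hours before ovulation, within 24 hours of it, 24 to 48 hours after, and more than 48 hours after. Exactly two inseminations can be placed in four rows in C(4+2−1, 2) = 10 ways: 4 with both in one row and 6 with one in each of two rows. One pattern matches the instruction (one within 24 hours, one 24 to 48 hours after). A second matches if the row before ovulation also counts for the first window. The count analysis pools all 10. This is a count of patterns, not of cycles, and it rests on the rows that are visible.

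**Step 3: how far the two-per-cycle rate could be from the on-schedule rate.** Let m be the mistimed share of the two-per-cycle group, and g the on-schedule pregnancy rate minus the mistimed rate within that group. Then

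rate in the group = (1 − m) × on-schedule rate + m × mistimed rate,

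so on-schedule rate − rate in the group = m × g.

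The documents give neither m nor g. Over assumed ranges, the difference in percentage points is:

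| g | m = 10% | m = 30% | m = 50% | m = 70% |
|---|---|---|---|---|
| 2 points | 0.2 | 0.6 | 1.0 | 1.4 |
| 5 points | 0.5 | 1.5 | 2.5 | 3.5 |
| 10 points | 1.0 | 3.0 | 5.0 | 7.0 |

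If timing makes no difference (g = 0), the difference is zero. The table shows what the assumptions imply and is not an estimate for this study.

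**The case against.** The strongest reply is that the hypothesis may be about count after all. Section 4.2 equates dosing with the instance of insemination, so a dosage schedule can be read as a number of inseminations. The alternate sentence speaks of a minimum of two, Section 6.1.2 recommends at least two, and its first window is only a preference. On that reading the count table answers the hypothesis and only the wording of the first sentence is loose. This stands in part: the contrast is not strictly exactly two on schedule against everything else. It does not remove the mismatch. The first sentence lists schedule and number as separate alternatives, Section 6.4 puts both windows into the minimum intervention, and Section 4.2 names timing alongside dosing.

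A second reply is that the general tests, or the exploratory model with a list that need not be complete, could take in timing. They could, but none is specified to do so.

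Third, the stated aims on timing are soft, and the regrouping could be done later without new data. That is fair and limits the weight of the point. Choosing the timing definition after seeing the data would, however, be weaker than fixing it now.

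A reader might infer from the one-in-ten pattern count that most two-insemination cycles are mistimed. The documents do not support that, since patterns are not equally likely and no shares are given. A reader might also infer that the plan ignores timing or adherence. It does not: Secondary Hypothesis 3 describes timing, and Sections 6.4 and 10.1.8 plan to determine whether use was as intended. What is missing is the link to pregnancy.

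**Conclusion.** The point holds and is minor. The analysis specified for Tertiary Hypothesis 3 cannot separate on-schedule from mistimed use among people with two inseminations per cycle, and no named analysis elsewhere does so against pregnancy. The count half of the hypothesis is examined; the schedule half is not.

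The size of any distortion cannot be derived from the documents, and the range of 0.2 to 7.0 points rests wholly on assumed inputs. The hypothesis is tertiary and its analysis mainly descriptive, so a reading in which a primary or secondary conclusion is put in doubt would go too far.

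The conclusion rests on reading Section 6.4 as the definition of the instructed schedule, and on the survey pages that are visible.

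**What to change.** Keep the table by 1, 2, 3 and 4 or more inseminations, and add one pre-specified comparison of pregnancy rate by on-schedule status.

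- **Definition.** On-schedule means at least one insemination in the within-24-hours row and at least one in the 24-to-48-hours-after row of the Appendix A grid. Three or more are allowed, in line with the minimum-of-two wording.
- **Sensitivity checks.** (a) Restrict on-schedule to exactly two inseminations. (b) Also accept the row for 24 to 48 hours before ovulation as meeting the first window.
- **Untimed users.** Report respondents who say they did not time ovulation in a separate row.
- **Unit and pregnancy link.** Use the same rule for assigning pregnancy to a cycle as the count table, and state it. If cycles are the unit, use standard errors clustered by respondent, since one person can contribute up to six. If pregnancy cannot be tied to a cycle, report the comparison per respondent, as descriptive only.
- **Wording.** Make the two sentences of Tertiary Hypothesis 3 state the same contrast.

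The cost is a short addition to Section 9.1 and a recode of the grid. The visible pages suggest that no new question is needed, but the link between pregnancy and cycle must be confirmed first: the visible pregnancy question does not ask which cycle, and some survey pages are not shown. The drawbacks are smaller groups and some misclassification, because the survey windows refer to ovulation while the instruction refers to its first signs and its confirmation.
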